6.9 CRITERIA AND PROCEDURES FOR SUBJECT WITHDRAWAL

Subjects will be informed about their right to withdraw from the study at any time and for any reason without sanction, penalty, or loss of benefits to which the subject is otherwise entitled. Withdrawal from the study will not jeopardize their future medical care or

Clinical Investigational Plan

relationship with the investigator. Subjects will be asked to specify the reason for the termination, but have the right not to answer.

The investigator may decide to withdraw a subject from the study at any time with reasonable rationale. The subject's future care will not be influenced by a withdrawal, voluntary or otherwise, from the study. All reasonable efforts should be made to retain the subject in the clinical study until completion of the study.

Reasons for subject's withdrawal may include, but are not limited to:

- Subject refuses to continue participating in the study
- Research drug is not initiated by post-operative day 15
 - Subject non-compliance
- Subject participation is terminated by the investigator, as participation is no longer medically appropriate, even though the subject has provided consent
- Subject is lost to follow-up, or can no longer be tracked for data collection at a participating center. This does not apply to missed visits. Site personnel should at all times make all reasonable efforts to locate and communicate with the subject in order to achieve subject compliance to the scheduled follow-up visits:
 - The subject will be considered lost to follow-up after missing two consecutive visits; however, the PI or designated site personnel must document a minimum of two phone calls over a period of two consecutive weeks to demonstrate efforts to communicate with the subject. These phone calls will be documented in the subject's hospital records.
 - If these attempts are unsuccessful, a letter will be sent to the subject's last known address or general practitioner (GP) and a copy of the letter will be maintained in the subject's hospital records.

Note: If a subject does not attend a scheduled follow-up visit within the visit window, this will be considered a missed visit. The subject should attend the next scheduled visit and will not be excluded from the study.

If a subject withdraws from the study, the reason for withdrawal will be documented if available.

If subject withdrawal is due to an adverse event, the subject will be followed until resolution of the event or a determination has been made that the subject's condition is stable. The status of the subject's condition will be documented at the time of withdrawal.

When a subject is withdrawn for any reason, there are no withdrawal procedures to be performed, but all follow-up visits, study assessments, and research drug will be immediately stopped. The physician will resume management according to SOC. Withdrawn subjects should return all remaining research drug to the site. Refer to **Section 5.3.5** for the return of unused study drug.

Clinical Investigational Plan**7 ADVERSE EVENT AND COMPLAINT REPORTING****7.1 DEFINITIONS****7.1.1 ADVERSE EVENT**

An adverse event (AE) is any untoward medical occurrence, unintended disease or injury, or untoward clinical signs (including abnormal laboratory findings) in subjects, users or other persons, whether or not related to the investigational medical device.

This definition includes AEs related to the medical device, the research drug, and study procedures.

For this study, data for specified AEs will be collected as follows:

- Neurological Dysfunction, including hemorrhagic stroke, ischemic stroke, and/or TIA
 - Pump Thrombosis
 - Major Bleeding
 - Hemolysis
 - Major Infection
 - Right Heart Failure

Refer to **Appendix D** for a detailed description of each type of AE.

7.1.2 SERIOUS ADVERSE EVENT

A serious adverse event (SAE) is an adverse event that:

- Led to death
- Led to serious deterioration in the health of the subject, that either resulted in:
 - A life-threatening illness or injury, or
 - A permanent impairment of a body structure or a body function, or
 - In-patient or prolonged hospitalization, or
 - Medical or surgical intervention to prevent life-threatening illness or injury or permanent impairment to a body structure or a body function,
- Led to fetal distress, fetal death or a congenital abnormality or birth defect.

Note: Planned hospitalization for a pre-existing condition, or a procedure required by the CIP, without serious deterioration in health, is not considered an SAE.

7.1.3 PROCEDURE FOR ASSESSING, RECORDING, AND REPORTING ADVERSE EVENTS AND SERIOUS ADVERSE EVENTS

Investigators are responsible for the safety surveillance and reporting for the study. Safety surveillance begins at implant and after-the-fact reporting for all enrolled subjects will occur at the time enrollment and will continue until the subject has been withdrawn, experienced an outcome, or completed the study.

Clinical Investigational Plan

Investigators are responsible for reporting AEs to the Sponsor in a timely manner through the EDC, as well as for reporting applicable AEs to their IRB in accordance with their institutional requirements, national and local laws and regulations.

AEs will be followed until they are adequately resolved. Records relating to the subject's subsequent medical course must be maintained until the event has subsided, or until the event stabilizes and the overall clinical outcome is determined. The Sponsor may request de-identified source documentation as applicable.

There are known and anticipated AEs associated with LVAD therapy. These AEs along with detailed definitions can be found in the HM II IFU.

All suspected and confirmed pump thrombosis events will be adjudicated by an independent committee.

The Sponsor will ensure that all events are reported to the relevant authorities in accordance with applicable regulations.

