4.10 POINT OF ENROLLMENT

Subjects are considered enrolled in the study when subject consent has been provided, the HM II LVAD implant has been successfully completed, and the subject has been randomized to a research drug arm. Enrollment reporting and randomization must occur immediately when the subject leaves the operating room or no later than 48 hours following implant. An enrollment is reported to the Sponsor upon submission of the Implant and Randomization CRFs in the EDC. The follow-up assessment schedule is based on Day 1 being the date that the implant was completed.

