⁷ Subject is considered enrolled when inclusion/exclusion criteria are met; has been successfully implanted with a HM II LVAD; and has been randomized to a research drug arm (Treatment or Control).

⁸ Within the first 21 days post implant.

⁹ Best view available between Implant and Month 1 visit.

Clinical Investigational Plan**6.2.1 ANTIPLATELET TESTING AND PLATELET FUNCTION TESTING**

Subjects in both the Treatment and Control Arms will receive ASA resistance testing (e.g. TEG® PlateletMapping®, VerifyNow®, etc.) at the baseline visit. After obtaining informed consent, testing will be performed prior to implantation, and may require a brief administration of ASA (recommended 3-5 days) to subjects who are not currently on ASA therapy. Testing should be timed adequately prior to surgery so as not to effect subjects' ability to reach post-operative hemodynamic stability.

To retain investigator and patient blinding to the test results, all site labs should be directed to return de-identified (patient screening ID only) ASA resistance test results at the Sponsor's expense to the Sponsor. Results will not be entered into the subject's hospital record to protect blinding.

While the subject is on the research drug, antiplatelet testing or platelet function testing should not be performed, as it may result in un-blinding of the subject or the investigator. Un-blinding of the subject or investigator will be considered a CIP deviation and the subject will be withdrawn from the study.

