6.3 SCREENING AND ENROLLMENT

All patients who are screened for eligibility will be documented in the PREVENT II Screening Log and assigned a Screening ID number. To protect patient privacy, no identifying information will be recorded.

The Sponsor may request copies of the Screening Log throughout the study, but the ongoing log will be maintained on site.

Patients who qualify to participate in the study will be approached to discuss the study, consider voluntary participation, and, if applicable, provide informed consent. For patients who do not qualify to participate in this study, the reason for ineligibility will be entered in the screening log. For enrolled subjects, the assigned Subject ID number will be entered in the screening log. Patients with an Impella® device must have the device removed during HMII implant to be enrolled into the study.

Qualified subjects who have provided consent will be entered in the appropriate EDC CRF, which must be submitted to the Sponsor after the patient has been screened and prior to enrollment, or no later than 48 hours post implantation. Notification of enrollment to the Sponsor will only take place when the consented subject has been entered in the EDC. Enrollment information (name of the study, date of consent, and inclusion/exclusion criteria) will be recorded in the subject's hospital records.

If a consented subject does not meet all eligibility criteria at the time of implant; does not receive a HM II LVAD; experiences a serious adverse event in the perioperative period that the investigator feels would compromise the patient's participation in the trial (e.g., debilitating stroke); or expires during the implant procedure, then the subject will not be enrolled or contribute to the study endpoints. The reason for ineligibility at the time of

Clinical Investigational Plan

implant will be recorded in the screening log. The subject is enrolled upon successful implantation of the HM II and randomization per **Section 4.10**.

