12 STATISTICAL CONSIDERATIONS

PREVENT II is a prospective, multi-center, randomized, double-blinded, placebo-controlled study evaluating the risk of subjects over 50 years of age being managed on warfarin therapy alone compared to warfarin and ASA therapy together. The two groups in the study are as follows:

- 1) Treatment Arm: Warfarin (INR target: 2.0-2.5, median: 2.25) + Placebo (1 pill/day)
- 2) Control Arm: Warfarin (INR target: 2.0-2.5, median: 2.25) + ASA therapy (81mg/day)

In general, continuous data will be presented as the number of subjects, mean with standard deviation, median, minimum, and maximum values. Categorical data will be reported as frequencies and percentages. Adverse events will additionally be reported as events per subject year, with only those events that start after implantation of the HM II analyzed. The adverse events will be compared between the two arms of the study using risk ratios (Poisson's regression). Survival data will be presented and analyzed using the Kaplan-Meier method.

The primary endpoints will be analyzed per protocol method as defined in **Section 12.1**. Every effort will be made to avoid crossovers, but in such instances, analysis will be performed in accordance with **Section 12.1**. The study will be conducted in a double-blinded fashion with neither the investigator, nor the subject having the knowledge of whether the subject is in the Treatment or the Control Arm. Only the primary statistician from the Sponsor will have knowledge of the specific groups, and all other parties will be blinded.

Every effort will be made to collect all required data. A one-sided 0.025 level of significance or two-sided 0.05 level of significance will be used to declare statistical significance as outlined below. Multiplicity adjustments will not be made unless specified below. A sensitivity analysis will be performed to account for any bias that may have been introduced by subjects withdrawing from the study or being removed from the study.

Clinical Investigational Plan**12.1 STATISTICAL DESIGN, HYPOTHESES, METHOD AND ANALYTICAL PROCEDURES**

Subjects will be block randomized per site on a 1:1 ratio into the Treatment and Control Arms. The study is designed to satisfy two primary endpoints. Both primary endpoints must be met for the study to be successful.

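### Adverse events between study-directed aspirin for the baseline test and implant, and non-fatal events in consented subjects never enrolled, are not collected at study level

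*Combined protocol and SAP*

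**What the plan says.** Section 6.2.1 makes the baseline aspirin test universal: "Subjects in both the Treatment and Control Arms will receive ASA resistance testing". It takes place after consent and before implant, and it "may require a brief administration of ASA (recommended 3-5 days) to subjects who are not currently on ASA therapy".

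Section 7.1.1 defines an adverse event and adds: "This definition includes AEs related to the medical device, the research drug, and study procedures". It then names six categories for data collection: neurological dysfunction, pump thrombosis, major bleeding, hemolysis, major infection and right heart failure.

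Section 7.1.3 sets the start of surveillance and the population: "Safety surveillance begins at implant and after-the-fact reporting for all enrolled subjects will occur at the time enrollment". Section 4.10 says who is enrolled: "Subjects are considered enrolled in the study when subject consent has been provided, the HM II LVAD implant has been successfully completed", and randomisation has also taken place, no later than 48 hours after implant.

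Section 6.3 lists consented people who drop out before that point. They include those who receive no HM II, those who die during the implant procedure, and anyone who "experiences a serious adverse event in the perioperative period that the investigator feels would compromise the patient's participation in the trial". For all of them the rule is "then the subject will not be enrolled or contribute to the study endpoints", and the reason for ineligibility goes into the screening log.

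In Table 1 the Adverse Events row is blank at Baseline and Implant. It is marked from Week 1 to Month 12 and in the as-occurs column. Section 12 reports adverse events "with only those events that start after implantation of the HM II analyzed".

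**The concern.** The baseline test is a study procedure. Its results go to the Sponsor and are kept out of the hospital record, and they are not an eligibility criterion. Any aspirin given only so that the test can be done is therefore an exposure imposed by the research, shortly before major surgery. The trial's own rationale (Section 2.3) is that aspirin may raise bleeding in these patients.

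The adverse event definition brings harm from that exposure into scope. The reporting, scheduling and analysis rules then leave out the period in which the exposure occurs. If a subject bleeds on the third day of test-driven aspirin, a site following the protocol has no study form for the event. The Steering Committee would not see it, and the final report could show no procedure-related harm before implant because none was collected. What is at stake is subject protection and the completeness of the safety record.

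**Working it through.** The plan gives no figure to reproduce and no arithmetic applies. The check places the windows in order and follows each kind of subject through them.

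**Timeline**

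1. Consent (Section 4.9).
2. Study-directed aspirin if the subject is not already on it, recommended for 3 to 5 days (6.2.1).
3. Resistance test (6.2.1).
4. Implant, when safety surveillance starts (7.1.3).
5. Randomisation within 48 hours, which completes enrollment (4.10, 12.4).

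Reporting in Section 7.1.3 looks back from enrollment (step 5) to implant (step 4) and no further. The as-occurs column of Table 1 states no start date of its own, so the only start date available is the one in 7.1.3. Section 12 cuts the analysis at the same point.

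**Four cases**

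| Subject and event | Study-level record | Analysis and review |
|---|---|---|
| Later enrolled; event starts between first test dose and implant | None specified: precedes surveillance, no Baseline or Implant entry in Table 1 | Excluded by Section 12; no route to the Steering Committee |
| Enrolled; event starts at or after implant | Collected: major bleeding (7.1.1, Appendix D, with a transfusion criterion for the first 7 days); transfusions at implant (Table 3) | CEC adjudicates bleeding (Section 14); events associated with the primary endpoints go to the Steering Committee (12.3). No rule asks whether the test dose contributed |
| Consented, never enrolled; non-fatal event | At most a reason in the screening log (6.3), held on site, with copies to the Sponsor on request | None |
| Consented, never enrolled; death | Reportable to the Sponsor under 7.1.4, which states neither a start date nor an enrollment condition; 6.3 calls these people subjects | None specified |

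**Length of the uncovered window** for a subject who is later enrolled: the recommended 3 to 5 days of aspirin, plus any interval between test and surgery. Section 6.2.1 asks for adequate timing before surgery but states no interval.

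**Conflict.** Section 7.1.1 puts events related to study procedures in scope with no time limit. Sections 7.1.3 and 12 and Table 1 together leave the first and third rows without collection, analysis or review.

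**The case against.** The strongest reply is that the main hazard of aspirin given days before surgery is perioperative bleeding, and in enrolled subjects that is collected and adjudicated. This stands. A reader might infer that harm from the test dose is never captured or reviewed; the documents do not support that. What is missing for these events is attribution to the test dose, which is a narrower matter.

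Other routes also exist. Deaths are reportable under 7.1.4. Section 7.1.3 requires applicable events to go to the local IRB. The Anticoagulation/Antiplatelet Medications Log is marked at Baseline, so the exposure itself can be documented. A disqualifying perioperative SAE leaves a screening-log reason. These points stand, but none is study-level collection: IRB reports are local, are not pooled across up to 45 sites, and have no stated path to the Steering Committee, while a log reason is not an event record.

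Known aspirin allergy is an exclusion, and testing is to be timed ahead of surgery. Both lower the risk; neither detects an event. Allergic reaction is not one of the six collected categories at any time, so its absence before implant does not come from the surveillance start date and is not evidence for this point.

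Three further inferences should be resisted:

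- **That the subjects most harmed by the aspirin are the ones removed.** Nothing in Section 6.3 links its reasons for non-enrollment to test-driven aspirin.
- **That a large, known number are exposed.** Assuming 20% to 50% not on aspirin gives 350 × 0.20 = 70 to 350 × 0.50 = 175. The documents give no such share, 350 is a maximum, and testing only may require aspirin.
- **That subjects are not told of the exposure.** The sample consent is provided separately.

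**Conclusion.** The point holds in bounded form. Adverse events that start between the first study-directed aspirin dose and implant, and non-fatal events in consented subjects who are never enrolled, are not collected, analysed or reviewed at study level. Section 7.1.1 says events related to study procedures are in scope, so the sections contradict each other.

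The number exposed, the dose given for the test and the event rate are all absent from the documents, so no estimate of harm can be made. The conclusion does not depend on them: it follows from the text of the rules, assuming sites apply 7.1.3 and Table 1 as written.

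A reader might also infer bias between arms. The documents do not support this: the aspirin precedes randomisation and is given regardless of the later assignment, so the arm comparison on the two primary endpoints is not biased by this gap. This is a subject-safety and data-completeness issue that should be corrected; it does not threaten the primary analysis.

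**What to change.** Reconcile Sections 6.2.1, 7.1.1 and 7.1.3 and Table 1:

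- For any consented subject given aspirin for the baseline test, report major bleeding, SAEs and death to the Sponsor from the first study-directed dose until randomisation or the decision not to enrol, whether or not the subject is enrolled.
- Add the matching adverse-event entries at Baseline and Implant in Table 1, with a footnote limiting the Baseline entry to these subjects.
- State how the Major Bleeding definition applies before implant, since its transfusion criteria in Appendix D are timed from implant.
- List these events separately from the primary endpoints, outside the Section 12 event-rate analysis, and include the listing in the Steering Committee reviews already planned in Section 12.3.

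The cost is protocol wording and one short form. Section 6.3 already has qualified consented subjects entered in the EDC around the time of implant, so a place for the data exists. No visit, sample size, endpoint or treatment rule changes. The small downside is some data entry for subjects who are never enrolled.

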7.1.4 SUBJECT DEATH

All subject deaths will be documented and reported to the Sponsor in a timely manner after the investigator becomes aware of the event.

The Sponsor may request de-identified source documentation as applicable. Additional information may be requested, when required, by the Sponsor in order to support the reporting of deaths to regulatory authorities.

The PI or designated site personnel must notify the IRB, if appropriate, of the deaths reported to the Sponsor in accordance with national and local laws and regulations.

7.2 COMPLAINTS

During the study, the investigator will be responsible for reporting all complaints. A complaint means any written, electronic, or oral communication that alleges deficiencies related to the identity, quality, durability, reliability, safety, effectiveness, or performance of a device after it is released for distribution.

If the complaint does not involve an AE, the investigator must notify the Abbott Post-market Surveillance Department by entering complaints information into the Thoratec® Connect™ System or by calling the HeartLine™ at [name] as soon as possible after becoming aware of the complaint. Please contact the local Abbott representative to coordinate product returns as applicable. This information will not be collected on a CRF for the study.

If the complaint involves an AE, the investigator must complete an AE Case Report Form (CRF) including the information on the complaint and report to Abbott as soon as possible.

Should a subject death be caused by the Abbott device or the device contributed to the death, the investigator should complete a Form 3500A (MedWatch) and submit to Abbott and the FDA within 10 days after becoming aware of the event.

Clinical Investigational Plan**8 COMPLIANCE TO CIP****8.1 STATEMENTS OF COMPLIANCE**

The investigator will not begin subject enrollment or request informed consent from any subject prior to obtaining IRB approval and authorization from the Sponsor in writing for the study.

In case additional requirements are imposed by the IRB, those requirements will be followed, if appropriate. If any action is taken by the IRB, and regulatory requirements with respect to the study, that information will be forwarded to the Sponsor.

8.2 ADHERENCE TO THE CLINICAL INVESTIGATION PLAN

A deviation is defined as an event in which the investigator, site personnel, Sponsor or Sponsor representative did not conduct the study in accordance with the CIP, IRB requirements, or the Investigator Agreement. The investigator is not allowed to deviate from the CIP, which includes inclusion/exclusion criteria and protection of subject safety, except as specified under emergency circumstances. Investigators and sites agreeing to participate in the study must believe that there is equipoise for randomization, and must be willing to be blinded for the duration of the study at their site. Un-blinding will not be performed unless subject is experiencing a major allergic reaction potentially attributable to the research drug, and will require Steering Committee approval. If the study drug is un-blinded, then the subject will be withdrawn from the study.

